10.3.2 Subject Disposition and Characteristics

10.3.2.1 Subject Disposition

Summary tables by treatment group and total population will present:

- The number of subjects enrolled into the study (ie, signed the ICF).
- The number of subjects who prematurely discontinued investigational product.
- The number of subjects who were withdrawn from the study.
- The number of subjects who completed the study.

Reasons for discontinuing the investigational product and withdrawing a subject from the study will be listed by subject.

10.3.2.2 Subject Characteristics

At minimum, subject characteristics will be presented in summary tables. Descriptive statistics will be presented for continuous data and categorical data as described above. Age will be described as both a continuous and a discrete variable. Supportive data will be listed by subject.

10.3.3 Safety Analyses

TEAEs will be coded using the Medical Dictionary for Regulatory Activities (MedDRA) version 24.1 (or higher). A TEAE is defined as an AE reported at or after the start of the first administration of study treatment. Only TEAEs will be summarized.

An overview summary of TEAEs, including counts and percentages of subjects with any of the following events, will be produced:

- TEAEs
- TEAEs related to study treatment
- TEAEs leading to permanent discontinuation of study treatment
- Serious TEAEs
- Serious TEAEs related to study treatment
- Fatal TEAEs

- Fatal TEAEs related to study treatment
- TEAEs by severity
- Treatment-emergent AESIs

TEAEs will be summarized by system organ class and preferred term. TEAEs will also be summarized by causality and severity. All TEAE summaries will be provided for each treatment group and overall.

The number and percentage of subjects with plasma anti-CSL312 antibodies will be summarized by treatment group and overall.

Laboratory evaluations (hematology, biochemistry, and urinalysis) will be summarized descriptively by treatment group.

Change from Baseline in DL_{CO} will be summarized using descriptive statistics by treatment group.

The Safety Analysis Set will be used for the safety analyses unless indicated otherwise.

10.3.4 Pharmacokinetics Analyses

Plasma concentrations of CSL312 will be summarized by nominal time point. The following descriptive statistics will be presented for plasma concentration summaries: number of observations (n), arithmetic mean, SD, %CV, median, geometric mean, geometric CV, minimum, and maximum.

The following PK parameters will be derived using non-compartmental PK analyses and will be summarized after SC administration of CSL312 at each SC dosing interval:

- C_{trough}
- C_{max} (last SC dosing interval only)
- T_{max} (last SC dosing interval only)
- AUC_{0-tau} (last SC dosing interval only)

The following PK parameters will be derived and summarized after the IV administration of CSL312:

- C_{\max}
- T_{\max}
- C_{trough}

The following descriptive statistics will be presented for all PK parameters except T_{\max} : n, arithmetic mean, SD, %CV, median, geometric mean, geometric %CV, minimum, and maximum. For T_{\max} , n, median, minimum, and maximum will be summarized.

The PK Analysis Set will be used for the PK analyses.

Additional information on the analysis of PK parameters will be provided in the SAP.

10.3.5 Pharmacodynamic Analyses

10.3.5.1 FXIIa-mediated Kallikrein Activity

Change from Baseline in FXIIa-mediated kallikrein activity over time will be calculated for each subject. The comparison of primary interest is the change from Baseline at Week 14. If the data are not normally distributed by visual inspection or statistical testing, an appropriate data transformation may be done. The data (or transformed data) will be compared between CSL312 and placebo using mixed-model repeated measure (MMRM), with treatment group and visit as fixed effects, and Baseline as a covariate. Analyses will be implemented using SAS PROC MIXED. Interactions with visit will be included for treatment group and Baseline. A restricted maximum likelihood (REML) approach will be used. An unstructured variance-covariance structure will be used to model the within-subject errors. This variance-covariance matrix will be estimated across treatment groups. If the model fails to converge, a heterogeneous Toeplitz structure (the TOEPH option in SAS PROC MIXED) will be used. The Kenward-Roger approximation will be used to estimate denominator degrees of freedom and adjust standard errors.

FXIIa-mediated kallikrein activity will be summarized by nominal time point with the following descriptive statistics: n, mean, SD, %CV, minimum, first quartile (Q1), median, third quartile (Q3), maximum, geometric mean, geometric %CV, and percent below the limit of quantitation (%BLQ). Individual FXIIa-mediated kallikrein activity-time profiles will be plotted using actual sampling times. Mean (\pm SD) FXIIa-mediated kallikrein activity profiles will also be plotted using nominal (planned) time points.

Observed change from Baseline and percentage of Baseline values of FXIIa-mediated kallikrein activity over time will also be summarized using descriptive statistics and presented graphically by treatment group.

A nonparametric Jonckheere-Terpstra test may be performed as appropriate to test the trend over time for each treatment group.

The PD Analysis Set will be used for this analysis. Additional information on the analyses of FXIIa-mediated kallikrein activity will be provided in the SAP.

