10.1 Sample Size Estimation

The sample size for this study was determined based on feasibility, not based on a power calculation. It was estimated that enrolling approximately 80 subjects (40 in each treatment group), and taking into account a 12% dropout rate, a total of 70 evaluable subjects (35 in each treatment group), would be considered sufficient for assessment of safety, PK, and biomarker profiles.

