10.3 Statistical Analyses and Methods

10.3.1 General Considerations

A complete description of the statistical analyses and methods will be provided in the statistical analysis plan (SAP), which will be finalized before database lock. In general, continuous variables will be summarized using descriptive statistics (number of observations [n], mean, SD, median, minimum and maximum. Categorical variables will be described using frequencies and percentages. For repeated observations of continuous variables, the change from Baseline will also be summarized.

All statistical tests will be 2-sided and will be performed at the 5% level of significance. Since no type I error adjustment will be performed for this study, all p-values will be considered nominal.

If not specified otherwise, Baseline refers to the last nonmissing measurement before the first administration of investigational product (CSL312 or placebo).

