10.3.7 Analysis of Exploratory Endpoints

10.3.7.1 Biomarker Analyses

All PD and biomarker data change from Baseline and percent change from Baseline in the blood will be analyzed using the same methodologies as described for FXIIa-mediated kallikrein activity (see [Section 10.3.5.1](#)). In addition, correlations between the change from Baseline for each PD and biomarker at Week 14 and each spirometry measurement of FVC (change from Baseline in FVC [mL] and in FVC percent predicted) measured at Week 14 may be investigated using a scatter plot, Pearson correlation coefficient and Spearman correlation coefficient by treatment group. All PD and biomarker data will be summarized and analyzed using the PD Analysis Set. Additional information on PD analyses will be provided in the SAP.

Additional exploratory biomarker analyses will be reported separately from the clinical study report (CSR).

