4.5.1 Independent Data Monitoring Committee

The roles and responsibilities of the independent data monitoring committee (IDMC) and the safety data review schedules are described in the IDMC charter. Operationally, since the IDMC is ad-hoc and can be triggered before SAS programming can be done to generate summary output, in this case, only data dump listings will be generated. Otherwise, those summary tables will be provided for the following (along with their supporting listings):

- Demographics;
- Treatment and exposure;
- AE overall summary, SAEs, AEs, AESIs.

Other safety analysis output as listed below, will be provided as data listings:

- Vital signs, physical exams and respiratory tests;
- Safety laboratory parameters / urinalysis;
- ECG;
- Medical history;
- Concomitant medication;
- Spirometry.

Please refer to [Sections 9, 10, and 11](#) of this SAP for descriptions of the analysis listed above.

5 Changes from the Protocol Planned Analyses

There are no changes to the planned analyses as previously documented in the CSP.

The definition of screened analysis set was slightly modified, please refer to Section 6.1.

6 Study Analysis Sets

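### The optional Jonckheere-Terpstra test of trend over time in Protocol 10.3.5.1 assumes independent groups, but the visits are repeated measures, so its p-value does not hold the stated 5% level

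*Protocol*

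**What the plan says.** Protocol 10.3.5.1 first makes the data longitudinal: "Change from Baseline in FXIIa-mediated kallikrein activity over time will be calculated for each subject". It then specifies an MMRM for the comparison of CSL312 with placebo, with Week 14 as the main time point, and accounts for the dependence between visits: "An unstructured variance-covariance structure will be used to model the within-subject errors". Near the end of the same section it adds: "A nonparametric Jonckheere-Terpstra test may be performed as appropriate to test the trend over time for each treatment group". It gives no blocking by subject, no permutation within subject and no adjusted variance for that test.

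Protocol 10.3.1 sets the level: "All statistical tests will be 2-sided and will be performed at the 5% level of significance". It also says: "Since no type I error adjustment will be performed for this study, all p-values will be considered nominal".

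Protocol 10.3.7.1 states that PD and biomarker data "will be analyzed using the same methodologies as described for FXIIa-mediated kallikrein activity".

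SAP 13.1 and 13.2 repeat the MMRM and the descriptive summaries but do not mention a Jonckheere-Terpstra test. SAP Section 5 states: "There are no changes to the planned analyses as previously documented in the CSP". SAP Section 3 lists the original protocol and Amendments 1 and 2 as its basis. The current protocol is Amendment 3, and it still contains the sentence.

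**The concern.** The Jonckheere-Terpstra test compares independent samples across ordered groups, and its null variance is derived on that basis. Run within one arm over time, the groups are visits and the same subjects appear in each. The MMRM in the same section allows for this dependence; the named trend test does not.

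The error has no fixed direction. If visits share a stable subject effect, the null variance is too large and the test is conservative. If neighbouring visits are more alike than distant ones, or subjects drift, the null variance can be too small and the test rejects too often. A reader of a reported p-value could not tell which applies. Because the SAP neither specifies nor withdraws the test, the choice to run it could be left until after unblinding.

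**Working it through.** **Inputs**
- Subjects per arm: n = 35 (Protocol 10.1). Check on the plan's own figure: 70 / (1 - 0.12) = 79.5, rounded up to 80, which matches the planned enrolment.
- Level: 5%, two-sided (Protocol 10.3.1).
- Time points (Schedule of Assessments): kallikrein activity at 11 visits (Days 1, 8, 15, 36, 43, 64, 67, 71, 78, 85, 92). Most other biomarkers, apart from Screening, at 5 visits (Days 1, 8, 36, 64, 92).
- Within-subject correlation: not given. It is an assumption throughout and is shown as a range.

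**The test.** With k visits, N = nk and J the count of later-visit values exceeding earlier-visit values over all visit pairs (ties count one half):
- mean of J = (N² - kn²) / 4
- variance of J = [N²(2N + 3) - kn²(2n + 3)] / 72

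For k = 11, N = 385:
- mean = (148,225 - 13,475) / 4 = 33,687.5
- variance = (148,225 × 773 - 13,475 × 73) / 72 = 1,577,698, SD about 1,256

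For k = 5, N = 175:
- mean = (30,625 - 6,125) / 4 = 6,125
- variance = (30,625 × 353 - 6,125 × 73) / 72 = 143,937.5, SD about 379

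These variances are correct only if the visits are independent.

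**Independence fails for changes from Baseline.** Every change shares the subject's baseline value. If raw values have equal variance σ² and common correlation ρ, then Var(change) = 2σ²(1 - ρ). The covariance of two changes is σ²(ρ - ρ - ρ + 1) = σ²(1 - ρ). Their correlation is 0.5 whatever ρ is, including ρ = 0.

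**Simulated rejection rate with no trend** (Gaussian complete data, n = 35, |Z| > 1.96, 2,000 replicates; Monte Carlo standard error near 5% is √(0.05 × 0.95 / 2,000) = 0.5 points):

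| Assumed structure | 11 visits | 5 visits |
|---|---|---|
| Independent visits | 4.95% | 6.1% |
| Compound symmetry 0.3 | 2.6% | 2.1% |
| Compound symmetry 0.5 | 0.65% | 0.75% |
| Compound symmetry 0.8 | 0.0% | 0.05% |
| AR(1) between adjacent visits, 0.5 | 15.7% | 7.8% |
| AR(1), 0.8 | 19.0% | 3.5% |
| AR(1), 0.9 | 13.5% | 0.75% |
| AR(1), 0.95 | 6.3% | 0.1% |
| Decay per week 0.5 / 0.8 / 0.9 | 15.1 / 20.4 / 16.3% | 8.1 / 8.9 / 6.4% |
| Subject-specific slopes, mean zero | 3.6 to 12.4% | 2.5 to 8.2% |

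The first row recovers roughly the nominal level. A repeat run gave 0-1.6% for compound symmetry 0.5-0.8 and 15-21% for AR(1) 0.5-0.8 with 11 visits.

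**Cross-check.** If Z has true SD s, the rejection rate is 2[1 - Φ(1.96/s)]. The simulated s was 0.73 for compound symmetry 0.5 (11 visits): 1.96/0.73 = 2.68, giving 0.7%. It was 1.51 for AR(1) 0.8: 1.96/1.51 = 1.30, giving 19%. Both agree with the table.

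**Power for a true 0.3 SD rise, compound symmetry 0.5 and 0.8.** The comparator is a per-subject slope tested by a one-sample t-test.
- 5 visits: 20.5% versus 48.5% at 0.5; 12.4% versus 87.7% at 0.8.
- 11 visits: about 40% versus 71-98%.

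**Candidate replacements, type I error**
- Per-subject slope t-test: 4.9-5.2% (11 visits) and 4.8-5.2% (5 visits) over the compound symmetry, AR(1) and random-slope cases run.
- Page's test: 4.8-6.0% under compound symmetry, but under serial correlation 16-32% (11 visits) and 8-16% (5 visits).
- A linear visit contrast from the MMRM was not simulated.

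**The case against.** The strongest reply is that the sentence is only permissive and the SAP has in effect let it lapse. The protocol defers full methods to the SAP, the SAP presents itself as complete, and its kallikrein, PD and biomarker sections contain only the MMRM and descriptive summaries. Not taking up an optional test can be read as consistent with declaring no changes, and running it later would be a deviation to report in the clinical study report. This lowers the weight of the point but does not settle it. The SAP neither mentions nor withdraws the test, and the later protocol amendment retains it.

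It is also true that the protocol does not give the implementation. A version blocked or permuted within subject would be a different test and would have to be specified.

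Four stronger readings are tempting, and the material does not support them.
- **That the test has almost no power.** Low type I error under compound symmetry does not imply this. For a 0.5 SD rise over 11 visits with compound symmetry 0.5, 0.7 and 0.9, power was 94%, 97% and 100%. An assumed 3 SD step after baseline was always detected. The loss is relative to a within-subject test and matters for small trends.
- **That the inflation applies to every biomarker.** The cross-reference in Protocol 10.3.7.1 may carry the test to other markers, but SAP 13.2 states how biomarkers are analysed without it. The 15-21% figure also belongs to 11 visits. On a 5-visit schedule, serial correlation gives roughly 0-9%.
- **That type I error well above 20% should be expected.** This would need subject-specific drifts of a size the documents do not supply.
- **That a trial conclusion is at risk.** There is no primary hypothesis (SAP 4.1.1), all p-values are nominal, and the treatment comparison rests on the MMRM.

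The nominal label in Protocol 10.3.1 does not answer the point, however. It concerns multiplicity, not whether the null distribution of a single test is right.

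**Conclusion.** The point holds as a minor one. Used as written, the test does not hold its 5% level, because its ordered groups are repeated visits of the same subjects. With 35 subjects, actual type I error is about 0-2% under compound symmetry 0.5-0.8 with either schedule, and about 15-21% under AR(1) 0.5-0.8 with 11 visits. With 5 visits, serial correlation gives roughly 0-9%. Power is reduced but not absent.

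These sizes rest on assumed correlation structures, Gaussian data and no dropout, so they show the direction and possible scale of the error and do not forecast it for this trial. That independence fails does not depend on them. The primary safety endpoints and the Week 14 MMRM comparison are unaffected. What remains is an unsuitable optional test in the protocol and an unresolved difference between protocol and SAP.

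**What to change.** Delete the sentence from Protocol 10.3.5.1 and record the removal in SAP Section 5.

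If a within-arm trend is wanted, specify one of the following in SAP 13.1 before database lock:
- a linear contrast across visits within each arm, taken from the planned unstructured MMRM; or
- a linear slope per subject, tested within each arm by a one-sample t-test.

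The contrast uses a model already being fitted. If that model falls back to the heterogeneous Toeplitz structure, the contrast then depends on that structure; the slope test does not. Either should be labelled descriptive of the arm and not a treatment comparison.

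Do not substitute Page's test. It is valid only if within-subject correlation is exchangeable, and it drops subjects with incomplete visits, where 12% dropout is planned.

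The cost is one deleted sentence and one SAP entry, or one extra contrast or slope summary. No new data, sample size or visits are needed.

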10.3.6 Pharmacokinetic / Pharmacodynamic Relationships

Population PK and PK / PD modelling will be explored, as feasible, for further time-dependent characterization of PK versus PD endpoints and / or safety and efficacy endpoints.

Population PK and PK / PD modeling will be specified in a separate PK modelling SAP and the results will be reported separately.

10.3.7 Analysis of Exploratory Endpoints

10.3.7.1 Biomarker Analyses

All PD and biomarker data change from Baseline and percent change from Baseline in the blood will be analyzed using the same methodologies as described for FXIIa-mediated kallikrein activity (see [Section 10.3.5.1](#)). In addition, correlations between the change from Baseline for each PD and biomarker at Week 14 and each spirometry measurement of FVC (change from Baseline in FVC [mL] and in FVC percent predicted) measured at Week 14 may be investigated using a scatter plot, Pearson correlation coefficient and Spearman correlation coefficient by treatment group. All PD and biomarker data will be summarized and analyzed using the PD Analysis Set. Additional information on PD analyses will be provided in the SAP.

Additional exploratory biomarker analyses will be reported separately from the clinical study report (CSR).

10.3.7.2 Pulmonary Function Data Analyses

Change from Baseline including absolute and percent predicted in FVC over time will be summarized using the same MMRM, with treatment group, and visit as fixed effects, and Baseline as a covariate. Interactions with visit will be included for treatment group and Baseline. Mean difference and its 95% confidence interval will be provided at each time point, assuming that the data is normally distributed. A plot of these variables over time will also be provided by treatment group. The number and proportion of subjects with $\geq 5\%$ or $\geq 10\%$ absolute or relative decline in FVC percent predicted at 14 weeks will be presented. The Safety Analysis Set will be used for this analysis.

10.3.8 Interim Analysis

No interim analysis is planned for this study.

11 Quality Assurance

The study may be subject to an audit by CSL, an authorized representative of CSL or inspections by an authorized health authority (eg, USA Food and Drug Administration [FDA]). Health authorities may request access to all study documentation, including source documents for inspection and copying, in keeping with local regulations. CSL will notify the investigator of any upcoming audit / inspection.

In the event of an audit, all pertinent study-related documentation must be made available to the auditors. If an audit or inspection occurs, the investigator at each study site will permit the auditor / inspector direct access to all relevant documents and allocate their time as well as the time of relevant staff to discuss the findings and any relevant issues.

12 Regulatory and Ethics Considerations

12.1 Regulatory Considerations

CSL or its agents will submit the appropriate documents to the local regulatory agencies and will await approval before study start.

This study will be conducted under an FDA investigational new drug application as well as clinical trial applications in multiple countries and documented in accordance with the applicable regulatory guidelines and requirements.

The procedures set out in this CSP are designed to ensure that CSL and the investigator abide by the principles of the current ICH GCP guideline on the conduct, evaluation and documentation of this study, as described in ICH Topic E6 (Guideline for GCP). The study will also be carried out according to all applicable international and national regulatory requirements.

12.2 Institutional Review Board / Independent Ethics Committee

The investigator must submit the CSP and ICFs for review by an authorized and properly constituted (according to local guidelines) IRB / IEC. Written approval must be received from the IRB / IEC before commencement of the study.

12.3 Subject Information and Informed Consent

Informed consent of study subjects according to the standards of GCP must be implemented in this clinical study before protocol-specified procedures are carried out. Information should be given in both oral and written form and should be deemed appropriate by the IRB / IEC. Subjects, their relatives (or if necessary, legally acceptable representatives) must be given ample opportunity to inquire about details of the study.

The subject (or if necessary, legally acceptable representatives) must be provided with a copy of the signed informed consent form.

Should there be any amendments to the CSP that would directly affect the subject's participation in the study (eg, a change in any procedure), the ICF must be amended to incorporate this modification. Subjects must be informed of the change and they must sign the amended ICF indicating that they re-consent to participate in the study.

12.4 Subject Confidentiality

All subject names and contact details will be kept confidential. Subjects will be identified throughout documentation and evaluation by the number allotted to them during the study. Each subject will be told that all study findings will be handled in the strictest confidence.

The investigator at the study site will be responsible for retaining sufficient information about each subject (eg, name, address, phone number and identity in the study) so that regulatory agencies or CSL may access this information should the need arise. These records should be retained in a confidential manner as long as legally mandated according to local requirements.

Subject medical records pertaining to the study may be inspected / audited at any time by CSL employees or their duly authorized representatives, a health authority or the IRB / IEC. All records accessed will be strictly confidential. Consent to participate in the study includes consent to these inspections / audits.

